2.7 Rationale

TNBC represents a significant proportion of breast cancer patients, has poor prognosis in a considerable number of patients and, no targeted approach to therapy is available at this time. The luminal breast cancer type category derive major clinical benefit from agents target ER; this therapy improved cure rates in the adjuvant setting and prolonged disease control in the metastatic setting. Similarly, the HER-2-neu category have had substantial clinical benefit from targeting the HER-2 receptor plus chemotherapy including dramatic reduction in disease recurrence rate in the adjuvant setting and enhanced response rate and duration of response in the metastatic setting. Thus, new targeting agents in TNBC are needed!

As presented in the background, there is **strong provocative preclinical data** demonstrating the activity of the combination of an EGFR inhibitor (lapatinib) and a PARP inhibitor (veliparib) in basal-like breast cancer. These preclinical data provide a strong rationale for the testing of this combination in patients with metastatic or recurrent triple negative breast cancer in whom taxane and anthracycline therapy has failed.

In addition, the clinical data supports the hypothesis that the combination of lapatinib plus veliparib will be safe and have efficacy in patients with metastatic triple negative breast cancer. Because there is no suggestion in the published literature that the toxicities of the two targeted agents will overlap, the known active and non-toxic doses of both agents will be used. For lapatinib, the dose was chosen at 1250 mg daily as this is the current recommended dose used for breast cancer in combination with capecitabine.⁶⁹ We believe that combining this dose of lapatinib with veliparib will be better tolerated than capecitabine. The data obtained in this pilot study will be used to design a phase II clinical trial that will be conducted by the Translational Breast Cancer Research Consortium. The dose of veliparib at 200 mg BID is based on our preclinical studies where veliparib was given 100mg/kg twice a day orally with lapatinib 30mg/kg twice a day orally. No toxicity was observed in mice with this combination, and per AbbVie Oncology, the 100mg/kg twice a day dose is equivalent to the 200mg PO twice a day dose in humans. Single agent dosing of veliparib is currently at 400mg BID. Additionally, the 200mg twice a day dose is well tolerated in combination with radiotherapy concurrently.⁵⁶ Importantly, we have built in this trial a cohort with lower doses of both agents if toxicity is observed in the initial cohort using the standard doses described above.

3.0 STUDY DESIGN (Table 1 and Figure 7)

The study is an open-label, single arm, single institution, pilot clinical trial of Veliparib (a PARP inhibitor) in combination with Lapatinib (an EGFR inhibitor) in patients with pathologically confirmed TNBC (ER negative, PR negative, HER-2-Neu negative by IHC [0, 1] or FISH) who have not received prior therapy in the metastatic setting (but failed anthracyclines and taxanes in the

neoadjuvant or adjuvant setting) or who have failed prior chemotherapy in the metastatic setting (including anthracyclines and taxanes and no more than two prior regimens for metastatic disease as long as patients have adequate performance status – see Appendix B). The data obtained in this pilot study will be used to design a phase II clinical trial that will be conducted by the Translation Breast Cancer Research Consortium.

As described in **Figure 7**, patients will receive Lapatinib (1250 mg PO daily continuously) in combination with Veliparib (200 mg PO every 12 hours continuously). A cycle of therapy is defined as 28 days of PO therapy. Lapatinib will start Day 1 cycle 1 and Veliparib will start on Day 2 Cycle 1 (for better understanding of the PK of the drugs as well as to induce a DSB repair defect first with Lapatinib). Dose reductions of Lapatinib and Veliparib will be allowed. Patients developing grade 1 and 2 toxicities will be permitted to take a drug holiday of up to 14 days; after the drug holiday, if the adverse event has resolved to the satisfaction of the investigator, the study drugs may be resumed at the same level. In the event of recurrent toxicity, there will be two dose reductions permitted (dose reduction minus one will be Lapatinib 1000 mg PO daily continuously and Veliparib 150 mg PO every 12 hours continuously); dose reduction minus two will be Lapatinib 750 mg PO daily and Veliparib 100 mg PO every 12 hours continuously. If the adverse event recurs after dose reduction two, the patient will be taken off the study. Patients developing grade 3 and 4 toxicities will be interrupted for up to 14 days; after the drug holiday, if the adverse event has resolved to the satisfaction of the investigator, the study drugs may be resumed at a reduced dose (Lapatinib 1000 mg PO daily continuously and Veliparib 150 mg PO every 12 hours continuously). If the adverse event recurs, the patient will be taken off the study.

The primary endpoint of the trial is safety of the combination of Lapatinib and Veliparib. Objective response rate (ORR) and progression free survival (PFS) will be secondary endpoint. Patients will be evaluated for response every 2 cycles (8 weeks) using the RECIST 1.1 criteria (see Appendix D); patients with stable disease, PR or CR may continue therapy until disease progression or intolerance to the combination. Patients with progressive disease (PD) at any time will go off the study. The total enrollment goal is 20 patients; patients will be enrolled in a single site (University of Alabama at Birmingham) over a projected 12-18 months accrual interval. A biopsy of an accessible metastatic lesion will be obtained in appropriate patients (see inclusion criteria). Tissue obtained in this trial will be analyzed for global gene array analysis or other comprehensive genomic analysis (“Next-Gen” genomic analysis) at UAB and HudsonAlpha Institute for Biotechnology, and immunohistochemistry (ER, PR, HER2, Ki67), biomarkers of DNA repair such as H2AX and BRCA localization, EGFR location and signaling, and apoptosis markers; data obtained from the biopsies will be correlated with ORR and PFS. Plasma DNA and serum levels of M30 will be obtained and correlated with the efficacy data. Adverse events (toxicity) will be assessed continuously while the patient is in active therapy with appropriate adjustments of Lapatinib and Veliparib doses as described above. The protocol will be approved by the UAB Institutional Review Board (IRB).

Figure 7: Treatment Plan

[figure not shown]

Table 1

Pre-study Evaluation (Section 4)	Therapy (Section 6)	Follow-up

Eligibility
 
 Pathologically confirmed ER/PR negative, HER-2-Neu negative (by IHC [0,1] or FISH) breast carcinoma – metastatic stage Measurable disease by RECIST 1.1 criteria (see Appendix D) Patients who have not been treated for metastatic disease or who have progressed on chemotherapy regimens in the metastatic setting are eligible Prior use of anthracyclines and taxanes in the adjuvant/neoadjuvant settings or metastatic disease is required. Adequate organ function PS: ECOG 0-2 (see Appendix B) Life expectancy > than 12 weeks At least 19 years of age Biopsy of metastatic lesion is mandatory, if appropriate 	
Lapatinib: 1250 mg PO daily continuously in combination with
 
Veliparib: 200 mg PO twice a day continuously. Veliparib starts Day 2 Cycle 1
 
A cycle is defined as a 28 day period. Initial evaluation for response will occur after 2 cycles of therapy; patients with stable disease, PR or CR may continue until disease progression or intolerance to the combination. Re-evaluation of tumor status (response) will occur every 2 cycles of therapy. Patients with PD at any time will be taken off study.
	
 Assessment of response every 2 cycles (clinical and imaging). Standard therapy toxicity monitoring. Lapatinib and Veliparib pharmacokinetics.

This trial includes a continuous assessment stopping rule in order to have a high probability of stopping early if the toxicity rate is unacceptably high, say 60%, while having low probability of stopping early if the toxicity rate is acceptable, say 30%. This rule is based on a Pocock-type boundary as described by Ivanova et al (Anastasia Ivanova, Bahjat F. Qaqish, and Michael J. Schell. Continuous Toxicity Monitoring in Phase II Trials in Oncology. Biometrics 61, 540–545, 2005). This stopping rule is considered a guideline with the final decision of termination of the study to be made by the data safety committee.

Table 2: Minimum number of toxicities (X) required to consider stopping the study after N subjects, for 20 patients

X	3	4	4	5	5	6	6	7	7	7	8	8	9	9	9	10	10	11
N	3	4	5	6	7	8	9	10	11	12	13	14	15	16	17	18	19	20

This rule will provide a probability of 0.10 of stopping early if the true toxicity rate is 30%. In that case the expected number of subjects on the trial will be 18.87 and the expected number of toxicities will be 5.7. If, on the other hand, the true toxicity rate is 60%, then the probability of stopping early is 0.87 with an expected sample size of 9.8 and 5.9 expected toxicities. Table 2 is the stopping guideline if 'X' out of 'N' has a pre-defined toxicity. As an example, if we enroll 3 patients and all have toxicity, then we will consider stopping the trial; if we enroll 6 patients and 5 patients have toxicity then the trial will be stopped.

Drug related toxicities for the safety analysis described above are defined as: a) any grade 3 or 4 non-hematologic toxicity except anorexia, alopecia, nausea, fatigue, fever without neutropenia; b) failure to recover to baseline (except alopecia) after delaying the next dose by more than 14 days; c) grade 3 or 4 neutropenia complicated by fever $\geq 38.5^0$ C or infection, or grade 4 neutropenia of at least 7 days duration; or d) grade 4 thrombocytopenia, or grade 3 thrombocytopenia complicated by hemorrhage. Toxicity evaluation of the patients enrolled in the trial will be done using the NCI Common Toxicity Criteria, Version 4.0, and will be presented to the Clinical Protocol Monitoring Committee (UAB Safety and Monitoring Plan).

If toxicity meets the stopping rule at any time during the first 5 patients enrolled in the pilot study (see table 2), the protocol will allow the investigators to open a new 20 patient cohort using Lapatinib 1000 mg PO a day and Veliparib 150 mg PO twice a day. The new cohort will follow the same rules used in the original cohort (Cohort -1). Patients developing grade 1 and 2 toxicities will be permitted to take a drug holiday of up to 14 days; after the drug holiday, if the adverse event has resolved to the satisfaction of the investigator, the study drugs may be resumed at the same level. In the event of recurrent toxicity, there will be one dose reduction permitted (dose reduction minus one will be Lapatinib 750 mg PO daily continuously and Veliparib 100 mg PO every 12 hours continuously). If the adverse event recurs after dose reduction two, the patient will be taken off the study.

Patient Selection Criteria

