5.1.5 Veliparib Dosing

The daily dose of Veliparib will be 200 mg PO every 12 hours continuously for 28 days (a cycle), starting on Day 2 Cycle 1. Patients developing grade 1 and 2 toxicities will be permitted to take a drug holiday of up to 14 days; after the drug holiday, if the adverse event has resolved to the satisfaction of the investigator, the study drug may be resumed at the same level. In the event of recurrent toxicity, there will be two dose reductions permitted (Veliparib 150 mg PO every 12 hours continuously and Veliparib 100 mg PO every 12 hours continuously). If the adverse event recurs, the patient will be taken off the study. Patients developing grade 3 and 4 toxicities will be interrupted for permitted for up to 14 days; after the drug holiday, if the adverse event has resolved to the satisfaction of the investigator, the study drugs may be resumed at a reduced dose (Veliparib 150 mg PO every 12 hours continuously). If the adverse event recurs, the patient will be taken off the study. **Veliparib will start on day 2.**

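### Grade 3–4 dose rules: Section 5.2.3 prints a lapatinib increase as the reduced dose, and the lower-dose cohort's only printed resumption dose is its own starting dose

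*Combined protocol and SAP*

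**What the plan says.** **Original cohort.** The start is lapatinib 1250 mg daily with veliparib 200 mg every 12 hours. After a grade 3–4 toxicity, Section 3.0 allows an interruption of up to 14 days, after which the drugs may be "resumed at a reduced dose (Lapatinib 1000 mg PO daily continuously and Veliparib 150 mg PO every 12 hours continuously"). It then adds: "If the adverse event recurs, the patient will be taken off the study". Section 5.1.5 repeats the veliparib half: "resumed at a reduced dose (Veliparib 150 mg PO every 12 hours continuously"). Section 5.2.3 gives the lapatinib half as 1000 mg every 12 hours, although its own first step for recurrent grade 1–2 toxicity is 1000 mg every 24 hours.

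**Lower-dose cohort.** If the stopping boundary is met during the first five patients, Section 3.0 lets the investigators "open a new 20 patient cohort using Lapatinib 1000 mg PO a day and Veliparib 150 mg PO twice a day". On its rules, the section says: "The new cohort will follow the same rules used in the original cohort (Cohort -1"). It then rewrites only the grade 1–2 pathway. After a drug holiday and recurrence, "there will be one dose reduction permitted (dose reduction minus one will be Lapatinib 750 mg PO daily continuously", with veliparib 100 mg every 12 hours. It closes: "If the adverse event recurs after dose reduction two, the patient will be taken off the study". Grade 3–4 toxicity is not mentioned for this cohort.

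**The concern.** Safety and tolerance are the primary objective, and dose modification after severe toxicity is the main protection for the individual patient.

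The Section 5.2.3 wording applies to every original-cohort patient with a grade 3–4 event. Taken literally, it raises lapatinib after a severe toxicity. Section 2.6 reports that 900 mg twice daily was less well tolerated than 500 or 750 mg twice daily, and that splitting the same daily dose in two doubles systemic exposure.

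The lower-dose cohort can open only after the higher dose has met the toxicity boundary. Its patients have the most need of a clear step down. As printed, recurrent grade 1–2 toxicity leads to a lower dose, while a first grade 3–4 event leads either to the same dose or to whatever the investigator chooses.

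**Working it through.** **Dose comparison.** Daily dose = mg per dose × 24 / interval in hours. Each percentage is relative to the starting dose of the same cohort.

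| Rule | Lapatinib, mg/day | Veliparib, mg/day |
|---|---|---|
| Original cohort, start | 1250 | 400 |
| Original, grade 3–4 step (3.0) | 1000 (−20%) | 300 (−25%) |
| Original, grade 3–4 step (5.2.3 and 5.1.5) | 1000 × 24/12 = 2000 (+60%) | 300 (−25%) |
| Lower-dose cohort, start (3.0) | 1000 | 300 |
| Lower-dose, grade 3–4 step if carried over from 3.0 | 1000 (0%) | 300 (0%) |
| Lower-dose, recurrent-toxicity step (3.0) | 750 (−25%) | 200 (−33%) |

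The grade 3–4 step in Section 3.0 is written in fixed milligrams, not as one level down. That is why it does not adapt to a cohort that already starts at that level.

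**What the other rules cover.**
- Section 5.2.2 stops lapatinib for severe liver changes and confirmed interstitial lung disease.
- Section 6.2.3 requires withdrawal for grade 3–4 LVEF decrease and grade 3–4 pneumonitis.
- Section 4.3 bars continuing on a single agent after unacceptable toxicity to the other, so these cases leave little or no veliparib resumption to specify.
- Appendix I reintroduces lapatinib at a reduced dose after grade 3 or complicated diarrhea.
- Appendix H advises considering a dose reduction for severe rash.

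None of these sets a two-drug resumption dose for other grade 3–4 events. The cytopenias are the clearest gap. Section 3.0 counts febrile or infected grade 3–4 neutropenia, grade 4 neutropenia lasting at least 7 days, and "grade 4 thrombocytopenia, or grade 3 thrombocytopenia complicated by hemorrhage" as toxicities. Less complicated grade 3–4 cytopenias are not counted, and they too have no stated resumption dose in this cohort.

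**How often the lower-dose cohort could open.** An exact binomial recursion over the printed boundary first reproduces the plan's own figures:

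| True toxicity | P(stop), computed / plan | Expected N, computed / plan | Expected toxicities, computed / plan |
|---|---|---|---|
| 30% | 0.098 / 0.10 | 18.87 / 18.87 | 5.66 / 5.7 |
| 60% | 0.872 / 0.87 | 9.76 / 9.8 | 5.86 / 5.9 |

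Within five patients the boundary is 3 of 3, 4 of 4 or 4 of 5. It is met either by three toxicities in the first three patients (p³), or by exactly one non-toxic patient among the first three followed by two toxicities (3p⁴(1−p)). So P = p³ + 3p⁴(1−p):
- p = 0.30: 0.0270 + 0.0170 = 0.044
- p = 0.40: 0.0640 + 0.0461 = 0.110
- p = 0.50: 0.1250 + 0.0938 = 0.219
- p = 0.60: 0.2160 + 0.1555 = 0.372

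These are upper bounds for opening the cohort, because Section 3.0 allows it but does not require it.

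**The case against.** The best defence is that no sensible investigator would act on either error. A dose described as reduced cannot be 2000 mg a day when the start was 1250 mg. Section 5.2.3 also tells patients to take five tablets once daily, and Appendix I treats a single daily dose as correct. Likewise, 1000/150 is not a reduction for a patient already taking it, and the lower-dose cohort has exactly one lower level. That cohort is optional, resumption is permissive, recurrence means removal, and the investigator can take a patient off at any time.

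Much of this stands. The intended doses are almost certainly 1000 mg every 24 hours and 750/100. A reader might infer that the plan means to rechallenge at full dose, or that lapatinib would double in the lower-dose cohort (2000/1000). The documents do not support either as a design intention. The first needs the least sensible reading of a reduced dose. The second applies a probable misprint to a cohort that may never open.

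What remains is that these are operative dosing instructions. Section 5.2.3 is where staff would look up the lapatinib dose. The 750/100 level is tied to recurrent toxicity directly after the grade 1–2 rule, whereas the original cohort's rules treat grade 3–4 separately. Inference by each investigator is a weak basis for dosing after a severe event.

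**Conclusion.** Both rules are wrong as written and should be corrected before they are used.

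1. The Section 5.2.3 error comes first, because it reaches every original-cohort patient with a grade 3–4 event: +60% lapatinib where −20% is meant. That it is a copying error is an inference, though a strong one.
2. The lower-dose cohort gap is narrower. Read literally, the carried-over step is a 0% cut. If only the stopping rules carry over, no general grade 3–4 step is stated. It matters only if the cohort opens (probability at most 0.044 at 30% and 0.372 at 60% true toxicity) and a patient then has an event outside the event-specific rules. The documents give no grade 3–4 rate for the combination, so no patient count can be given.

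It would go too far to say that severe toxicity in this cohort is unmanaged, since the event-specific rules cover many cases. It would also go too far to say that the stopping-rule count cannot be affected. A patient whose first event is counted is already in the tally whatever dose follows. A patient whose first grade 3–4 event is not counted, such as fatigue or uncomplicated grade 3 thrombocytopenia under the Section 3.0 definition, could later have a counted event that depends on the resumption dose. The boundary, sample size and analysis figures themselves do not change.

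**What to change.** - **Section 5.2.3:** change the lapatinib grade 3–4 dose to 1000 mg every 24 hours.
- **Section 3.0, lower-dose cohort:** add that a first grade 3–4 toxicity resolving within 14 days may resume only at lapatinib 750 mg daily and veliparib 100 mg every 12 hours, with removal from study if it recurs. State that the event-specific rules in Sections 5.2.2 and 6.2.3 and Appendices H and I still apply.
- **Sections 5.1.5 and 5.2.3:** limit the printed grade 3–4 doses to the original cohort.
- **Wording only:** the lower-dose cohort has one permitted reduction, so its removal sentence should refer to recurrence after this dose reduction, not after a second one.

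The cost is a short amendment: one or two sentences in Section 3.0 and a phrase or two in each of 5.1.5 and 5.2.3. It uses dose levels already in the protocol and changes no statistical figure.

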4.1 Inclusion Criteria

- Patients must have pathologically documented breast cancer which is stage IV.
- Tumor must be HER-2-neu negative (defined as 0 or 1+ staining by immunohistochemistry or gene amplification ratio ≤ 2.0 , by FISH), estrogen and progesterone receptors negative (< 1%). Patients with BRCA 1 or 2 mutations will NOT be included.
- Patients must have measurable disease, defined as at least one lesion that can be accurately measured in at least one dimension (longest diameter to be recorded) (RECIST criteria 1.1 – see Appendix D).
- Biopsy of a metastatic lesion is not required for protocol entry but all patients with reasonably accessible lesions (chest wall, breast, skin, subcutaneous, superficial lymph nodes, bones and liver metastases) must agree to biopsy (lung and brain metastasis will not be biopsied):

- Biopsies may be done with local anesthesia or intravenous conscious sedation, according to standard institutional guidelines.
- If a biopsy requires general anesthesia, then it is only allowed if acquisition of tissue is necessary for clinical reasons (i.e. is clinically indicated), and excess tissue that would otherwise have been discarded is then used for research purposes. If a biopsy requires general anesthesia, then a biopsy of that site for research purposes only, *without* a coexisting clinical indication is not allowed on this protocol.
- Patients with reasonably accessible lesions as described above, who will not agree with the biopsy, will not be enrolled in the trial.
- Patients with **NO** reasonably accessible lesions as described above can be enrolled in the trial.
- Prior Therapy:
 - No more than two regimens in the metastatic setting as long as patients have adequate performance status. Patients with no prior chemotherapy for metastatic disease may be included in the trial if they received anthracyclines and taxanes in the adjuvant or neoadjuvant settings. Chemotherapy naïve patients with metastatic disease must have failed anthracyclines and taxanes.
 - Chemotherapy treatment prior to enrollment must be discontinued for at least 3 weeks prior to study entry.
 - Patients must have completed radiation therapy at least 21 days prior to beginning protocol treatment.
- Patients must have recovered from all reversible toxicities related to prior therapy before beginning protocol treatment, and may not have any pre-existing treatment-related toxicities greater than grade 2. Patients must have < grade 2 pre-existing peripheral neuropathy.
- Patients may receive bisphosphonates; however, if used, bone lesions may not be used for progression or response.
- At least 19 years of age.
- Life expectancy of greater than 12 weeks.
- ECOG performance status ≤ 2 (See Appendix B).
- Patients must have normal organ and marrow function as defined below:
 - Absolute neutrophil count: $\geq 1,000/\mu\text{L}$,
 - Hemoglobin: $\geq 9 \text{ mg/dL}$,
 - Platelets: $\geq 100,000/\mu\text{L}$,
 - Total bilirubin: $\leq 1.5 \times$ institutional upper limit of normal,
 - AST(SGOT)/ALT(SGPT): $\leq 2.5 \times$ institutional upper limit of normal without liver metastases, OR, $\leq 5 \times$ institutional upper limit of normal if documented liver metastases,
 - Creatinine: $\leq 1.5 \text{ mg/dL}$, OR calculated creatinine clearance $\geq 40 \text{ mL/min}$ (calculated by the modified Cockcroft and Gault method).
- Ability to understand and the willingness to sign a written informed consent document.
- Use of an effective means of contraception in subjects of child-bearing potential.
- Negative serum or urine beta-HCG pregnancy test at screening for patients with childbearing potential.
- Ejection fraction must be $\geq 50\%$

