5.1.4 Adverse Events Associated With Veliparib

At present, there have been more than 800 patients exposed to ABT-888, however only one study tested this drug as a single agent. From this single agent study, conducted in subjects with cancer, the most common reported side effects ($\geq 10\%$) with veliparib as a single agent were: nausea (50), fatigue (43), anemia (32), hyperglycemia (27), lymphopenia (24), hypoalbuminemia (22), abdominal pain (22), diarrhea (22), decreased appetite (22), headache (20), low sodium (19), increases in liver enzymes (17), back pain (15), ascites (15), constipation (15), thrombocytopenia (12), leukopenia (12), dizziness (12), increased creatinine (10), dyspnea (12), insomnia (10), and dry mouth (10), hot flushes (10). Less frequent, but potentially severe events include dehydration (6.9). Based upon events of seizures in preclinical studies using high doses (much higher of what it will be used in this study) seizures are a potential risk; however, in ongoing clinical studies, uncommon events of seizure have been observed. In preclinical studies also it has been demonstrated that Veliparib absorbs ultraviolet light; therefore, the potential exists that Veliparib may contribute to a risk of reddening or tanning of the skin when exposed to direct sunlight. In addition, as with any drug, allergic reactions are a possibility from a simple rash to anaphylactic shock. Side effects on an unborn or nursing infant are not known; however, in preclinical studies harmful effects on fetal development have been noted in experimental pregnant animals.

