6.2.2 Pre-study Assessments

Informed consent will be obtained before study-specific screening evaluations are performed. Screening evaluations must be performed within 4 weeks prior to day 0.

Within the 4 weeks prior to therapy initiation patients will undergo baseline clinical evaluation (including history, physical evaluation, vital signs, and performance status) and all enrolled patients will undergo biopsy of a selected lesion according to the guidelines described in eligibility criteria. Additional pre-study evaluations include: CBC with differential and platelets, CMP (fasting), CA27.29, pregnancy test (within 7 days if indicated), tumor measurements by images or staging studies which are defined as studies contributing to response evaluation, e.g. CTs (chest, abdomen, and pelvis), MRI, bone scan, PET, or plain x-rays, EKG and echocardiogram, and concomitant medication assessment. The ejection fraction will be confirmed as normal before proceeding with the first dose of lapatinib.

Patients with reasonably accessible lesions as described above, who will not agree with the biopsy, will not be enrolled in the trial. Patients with NO reasonably accessible lesions as described above can be enrolled in the trial.

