7.4 Sample Size and Power Justification

This is a single arm pilot study to evaluate the safety of combination of Veliparib and Lapatinib in patients with metastatic TNBC. A total of 20 patients will be enrolled to evaluate the safety as treatment related toxicity rate and the objective response rate. The sample size is NOT determined by the statistical power but the feasibility and relative precision of estimate, e.g. standards error of the estimation is $\leq 10\%$. Assuming the acceptable toxicity rate with combination therapy is no more than 30%; then, we will be able to have two sided 95% exact confidence intervals ([Clopper-Pearson intervals](#)) of toxicity estimate from 11.8% to 54.3%. Meantime, this sample size will provide two-sided 95% exact confidence intervals ([Clopper-Pearson intervals](#)) of objective response rate estimation as follow:

Table 2 Exact 95% Confidence Interval for Response Rate Estimation

Response rate %	Confidence interval (lower) %	Confidence interval (Upper) %
20	5.73	43.66
25	8.66	49.10
30	11.89	54.28

If the response rate is equal or greater than 30%, we will propose a phase II trial to be conducted in the Translational Breast Cancer Research Consortium (TBCRC).

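### The hemoglobin entry limit in Section 4.1 is in mg/dL; read literally it equals 0.009 g/dL and that line excludes no one

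*Combined protocol and SAP*

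**What the plan says.** Section 4.1 (Inclusion Criteria) introduces its laboratory limits with "Patients must have normal organ and marrow function as defined below". The hemoglobin line reads "Hemoglobin: $\geq 9 \text{ mg/dL". The same list gives neutrophils and platelets per microliter, and it uses mg/dL once more, for renal function: "Creatinine: $\leq 1.5 \text{ mg/dL".

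Other parts of the plan bear on the point:

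- Also in Section 4.1, patients must have recovered from reversible toxicities of earlier treatment and "may not have any pre-existing treatment-related toxicities greater than grade 2".
- Section 6.2.2 requires the blood count at screening: "Additional pre-study evaluations include: CBC with differential and platelets, CMP (fasting), CA27.29". It gives no reporting unit and no threshold.
- Table 1 in Section 3.0 summarizes this part of eligibility only as adequate organ function.
- Section 5.1.4 lists the common single-agent effects of veliparib, beginning "nausea (50), fatigue (43), anemia (32". The list is introduced with a 10% cut-off, so I take the figures as percentages.
- Section 7.5.1 commits to presenting baseline laboratory data and their change at each visit.

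**The concern.** A laboratory limit for entry is a decision rule. It should separate patients who may start treatment from those who may not. Hemoglobin in mg/dL at a value of 9 cannot do that, because the number lies far below any value seen in a living patient.

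The setting gives the slip some weight. The primary objective is the safety and tolerance of the combination. Section 2.5 names the blood and bone marrow among the target organs of veliparib, and anemia is among its common listed effects. If the line were applied literally, patients could enter with low hemoglobin, and the anemia and laboratory-toxicity summaries would be harder to read.

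There is also a compliance problem. Section 8.4.3 requires the trial to be run as the approved protocol describes. Staff who apply a limit in g/dL depart from the text, and staff who apply the text have no hemoglobin screen. An eligibility audit against the written line could not find a hemoglobin violation.

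**Working it through.** The limit is not derived from other figures in the plan, so there is no calculation of the sponsor's to reproduce. The check is a unit conversion and a search for anything that corrects or replaces the line.

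**1. Conversion.** Input: limit of 9 mg/dL (Section 4.1). Since 1 g = 1,000 mg, 9 mg/dL ÷ 1,000 = 0.009 g/dL.

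**2. Who fails the line as written.** The documents give no hemoglobin distribution, so the values below are assumed for illustration. The ratio to the limit is (value in g/dL × 1,000) ÷ 9.

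| Assumed hemoglobin (g/dL) | In mg/dL | Ratio to the written limit | Passes? |
|---|---|---|---|
| 1 | 1,000 | about 111 | yes |
| 2 | 2,000 | about 222 | yes |
| 5 | 5,000 | about 556 | yes |
| 7 | 7,000 | about 778 | yes |
| 8 | 8,000 | about 889 | yes |
| 9 | 9,000 | 1,000 | yes |

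All pass. The factor of 1,000 is the gap between the two units at the same number, 9; against lower hemoglobin values the gap is smaller.

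**3. Does another section supply the limit?** No. Section 4.1 holds the only numeric hemoglobin rule, and no section states a hemoglobin value in g/dL. Table 1 and Section 6.2.2 give no number.

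**4. Do other entry rules exclude anemic patients?** In part. Section 4.1 bars treatment-related toxicity above grade 2 and requires recovery from reversible toxicity of prior therapy. Every patient must have had anthracyclines and taxanes (Sections 3.0 and 4.2), so treatment-related anemia is a natural case for these rules. Anemia from another cause, such as bleeding or marrow involvement, falls outside them.

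**5. Does the line feed any statistical quantity?**

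- The toxicity definitions in Sections 3.0, 7.1 and 7.6 name specified neutropenia and thrombocytopenia as hematologic events, not anemia. Anemia could count only through failure to recover to baseline after a delay of more than 14 days, which is itself relative to the patient's own entry value.
- Section 7.4 rests the 20 patients on feasibility and precision: "The sample size is NOT determined by the statistical power". The exact intervals and the stopping table use toxicity or response counts and the number of patients. None uses hemoglobin.

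**The case against.** The strongest reply is that no site would apply the line literally. It sits under a heading that asks for normal marrow function, and a limit of 0.009 g/dL is untenable on sight. Staff would probably read g/dL, and the documents do not show that anyone would be enrolled on the literal reading. That stands as a judgment on likelihood and keeps the point small. It does not make the criterion right: a numeric entry rule should not depend on readers silently changing its unit.

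Four stronger conclusions are tempting, and the documents do not support them.

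- A reader might infer that no anemic patient can be kept out of the trial. That is true of the hemoglobin line alone; the rules on prior-treatment toxicity in Section 4.1 still exclude some.
- A reader might describe the limit as a thousand-fold below any clinical value. The factor is 1,000 only against 9 g/dL.
- A reader might infer that later worsening cannot be told apart from the entry state. Section 6.2.2 and the Section 6.6 schedule require a blood count before treatment and on day 1 of each cycle; the cycle 1 count may be omitted only when earlier results are no more than 4 weeks old. With the change-from-baseline reporting in Section 7.5.1, the separation can be made. What remains is harder interpretation if entry values range widely.
- A reader might infer that the primary endpoint or the stopping rule is compromised. Anemia is not among the named toxicities, so the effect there is slight at most.

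It is also fair to say that nothing has been miscalculated. This is a wrong unit, not wrong arithmetic. An error in reading the text from PDF cannot be wholly excluded, but the line is complete and there is no sign of one.

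**Conclusion.** The point holds in a narrow form. As written, the hemoglobin line in Section 4.1 is a wrong decision threshold: it excludes no one, and the protocol has no other numeric hemoglobin rule to take its place. The literal gap is a factor of 1,000 between the written unit and the same number in g/dL.

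The gap in eligibility is anemia that is not related to prior treatment. Treatment-related anemia is covered, above grade 2 or while reversible and unrecovered, by the neighboring criterion. The practical effect is probably small, because staff are likely to read the unit as g/dL; that is an assumption about conduct, not something the documents state. That g/dL was meant is likewise an inference, from the implausibility of mg/dL for hemoglobin, and the sponsor must confirm it.

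**What to change.** The sponsor should confirm the intended unit and value and correct the unit in Section 4.1; mg/dL appears to be a slip for g/dL. Any study form that copied the line should be checked at the same time. The documents mention electronic case report forms (Section 8.4.2) and confirmation of eligibility (Section 6.2.1) but do not reproduce either form, so this is a precaution and not a known defect.

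The cost is a one-unit text correction, made through the amendment route in Section 8.1. It needs no new assessment and no change to the analysis.
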